8.7.2 Clinical laboratory evaluations

Clinical laboratory evaluations include serum chemistry, hematology, and urinalysis. For the purposes of summarization in both the tables and listings, all laboratory values will be presented in SI units. If a lab value is reported using a nonnumeric qualifier e.g., less than (<) a certain value, or greater than (>) a certain value, the given numeric value will be used in the summary statistics, ignoring the nonnumeric qualifier; but will be listed as is in the listings. Severity of abnormal laboratory results will be graded according to CTCAE v5.0.

All laboratory data obtained between screening visit and the end of study will be used for the laboratory safety analysis. Laboratory summaries will be provided including values measured during the follow-up period, where appropriate.

Visit value and change and from baseline during the treatment period will be summarized by treatment group using descriptive statistics for all laboratory parameters.

Abnormal clinical laboratory results will be summarized by treatment group and severity at subsequent visits following screening when clinical safety labs are performed. Abnormality will be determined according to the pre-specified criteria at each site (which may vary by sites) and flagged in EDC.

Subjects with graded laboratory values will be identified in listings, including patient information, visit date, severity of abnormality, relationship to study product along with specifics of the abnormal laboratory results and corresponding normal ranges (when applicable).

Resilience Government Services, ADM03820-001 Version: Final v4.0, Date: 11-SEP-2023
BST1302-SOP-T01/v1.0/2020 Page 23 of 26

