3.2. Study Outcome Measures

3.2.1. Primary Endpoints

- The occurrence of Serious Adverse Events following administration of ADM03820 to the final follow-up visit.
- The occurrence of Adverse Events from administration of ADM03820 to the final follow-up visit.

²⁰ Eroshenko, N., Gill, T., Keaveney, M. Church, et al., Implications of Antibody-Dependent Enhancement of Infection for SARA-CoV-2 Countermeasures. *Nature biotechnology*. 05 June 2020. https://www.nature.com/articles/s41587-020-0577-1

• The occurrence of changes from baseline in physical examination, vital signs and clinical safety laboratory values following administration of ADM03820 to the final follow-up visit.

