7.5.2. Safety Laboratory Tests

The following laboratory tests will be performed at Days 8, 15, 30, 90, 180, and 365.

Safety labs with a mild Grade 1 value will not exclude a subject from participation but will serve as their baseline value.

- Hematology: hemoglobin, WBC with differential, absolute neutrophil count and platelet count. MCV, MCH, MCHC, RDW, MPV, which are included in a complete blood count with differential, will not be graded.
- Chemistry: serum creatinine, BUN, calcium, total bilirubin, direct bilirubin, indirect bilirubin, alkaline phosphatase, PT, PTT, INR, ALT, AST, sodium, potassium, and total CK.
- Urinalysis: dipstick: Urine protein, blood and glucose must be negative or trace. Menstruating females failing with positive blood on urine dipstick may be retested following cessation of menses.

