11.3.3.2. Additional Safety Analyses

Vital signs, physical examinations, and clinical laboratory values, including change from baseline, will be summarized by dose cohort and control group.

Descriptive summary statistics for laboratory data at admission (baseline value) and each applicable post-dose visit, including change from the baseline value, will be calculated. Descriptive summary statistics for vital signs at screening (baseline value) and each applicable post-dose visit, including change from the baseline value, will be calculated. Shift tables, showing individual subject changes from baseline will be presented for laboratory parameters using toxicity grading. Subjects with Graded values of vital sign and laboratory parameters will be identified in listings.

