8.0 Changes to Planned Analysis from Study Protocol

Added per-protocol population in protocol section 11.3.1.

Resilience Government Services, ADM03820-001

BST1302-SOP-T01/v1.0/2020 Page 25 of 26

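### SAP 8.7.2's by-visit count of abnormal laboratory results rests on site-specific criteria and ignores the entry value, and the protocol's graded laboratory shift tables are not named in the SAP

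*SAP*

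**What the plan says.** Protocol 3.2.1 words the third primary endpoint as change from baseline: "The occurrence of changes from baseline in physical examination, vital signs and clinical safety laboratory values following administration of ADM03820 to the final follow-up visit". For laboratory data, protocol 11.3.3.2 asks for descriptive statistics including change from baseline, and also for a graded display by subject: "Shift tables, showing individual subject changes from baseline will be presented for laboratory parameters using toxicity grading".

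SAP 8.7.2 keeps the descriptive part: "Visit value and change and from baseline during the treatment period will be summarized by treatment group using descriptive statistics for all laboratory parameters". It also keeps grading: "Severity of abnormal laboratory results will be graded according to CTCAE v5.0". Its categorical display is a by-visit table: "Abnormal clinical laboratory results will be summarized by treatment group and severity at subsequent visits following screening when clinical safety labs are performed". The sentence that follows settles which results enter that table: "Abnormality will be determined according to the pre-specified criteria at each site (which may vary by sites) and flagged in EDC". The site criteria themselves are not given.

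Subjects can carry such results into the trial. Inclusion criterion 8 (protocol 5.1) admits out-of-range screening values that the investigator judges not clinically significant. Protocol 7.5.2 adds: "Safety labs with a mild Grade 1 value will not exclude a subject from participation but will serve as their baseline value".

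The SAP names shift tables once, for ECG (8.7.5). Its section 8.0 (numbered 9.0 in its table of contents) declares one change from the protocol's analysis: "Added per-protocol population in protocol section 11.3.1". SAP 1.0 places the table, listing and figure templates in a separate document, which was not available for this review.

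**The concern.** Two things other than the study product can put a subject into the SAP 8.7.2 table.

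- **The site's rule.** If two sites apply different criteria, the same value can be counted at one and not at the other. CTCAE does not repair this on the natural reading, because it grades results that have already been called abnormal.
- **The entry state.** A subject who starts with a mild abnormality that never changes is counted again at each later safety-laboratory visit, up to six times (Days 8, 15, 30, 90, 180 and 365).

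A graded shift table sets each subject's later grade against the baseline grade, which deals with the second problem directly. If grades are assigned by one rule, it reduces the first as well. That is the display the SAP text leaves out. At stake is whether a reader of the categorical laboratory results can tell new or worsened abnormalities from background in groups of eight, for a component of the primary endpoint.

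**Working it through.** **Inputs.** Eight active and two placebo subjects per cohort, five cohorts (protocol 4, SAP 3.0). Six post-dose safety-laboratory visits (protocol 7.5.2). True event rates of 0.15 to 0.5 in the sample-size rationale (protocol 11.1). Neither document gives the proportion of subjects entering with an abnormal result, or says how site criteria differ. The rates in steps 3 and 4 are therefore assumptions.

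**1. The plan's own figures.** The chance of at least one event in 8 is 1 − (1 − p)^8.
- p = 0.15: 1 − 0.85^8 = 0.728
- p = 0.5: 1 − 0.5^8 = 0.996
- Exact two-sided 95% upper bound for 0 of 8: 1 − 0.025^(1/8) = 0.369

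All three agree with protocol 11.1.

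**2. Weight of one subject.** 1/8 = 12.5%. Suppose 2 of 8 active subjects enter with a Grade 1 result for one parameter, both sites flag it, and nothing changes. The SAP table shows 2/8 = 25% abnormal at every visit, while a shift table shows 0 of 8 worsening. With 0 to 3 such subjects the SAP table runs from 0% to 37.5%, with no drug effect anywhere in that range.

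**3. Background alone.** Let p be the assumed proportion with a persisting entry flag on one parameter. The chance that at least one of 8 active subjects is counted is 1 − (1 − p)^8. The chance that this happens while neither placebo subject in the cohort is counted is [1 − (1 − p)^8] × (1 − p)^2.

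| Assumed p | At least 1 of 8 active | At least 1 active and 0 of 2 placebo |
|---|---|---|
| 0.02 | 0.149 | 0.143 |
| 0.05 | 0.337 | 0.304 |
| 0.10 | 0.570 | 0.461 |
| 0.15 | 0.728 | 0.526 |
| 0.20 | 0.832 | 0.533 |

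At p = 0.15, background alone gives the same 0.728 that protocol 11.1 quotes for detecting a true 15% toxicity.

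**4. Site rules.** If one rule flagged 5% and another 10% (assumed), the expected count in 8 active subjects would move from 8 × 0.05 = 0.4 to 8 × 0.10 = 0.8 with no change in any subject.

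**5. Which outputs are touched.**

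| Planned laboratory output | Uses the site flag? | Takes account of the entry value? |
|---|---|---|
| By-visit abnormal results (SAP 8.7.2) | Yes | No |
| Visit value and change from baseline (SAP 8.7.2) | No | Yes |
| Laboratory-abnormality AE category (SAP 8.7.1) | Not stated | Yes, through the AE rule that only worsening of a screening condition is recorded |
| Baseline categorical summary (SAP 8.4.2) | Not stated | Shows entry state by group, not linked to later results by subject |
| Graded shift tables (protocol 11.3.3.2) | Not named in SAP text | Would do so, by subject |

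**The case against.** The strongest reply is that the endpoint, as worded, is still analysed. Change from baseline is summarised for every laboratory parameter without using the site flag. Severity is still graded by CTCAE v5.0, and graded values are listed with normal ranges. The AE category in SAP 8.7.1 is relative to baseline by rule, and SAP 8.4.2 tabulates the entry state. No test is run on safety endpoints, and the dose-escalation criteria in protocol 9.5 rest on graded AEs and committee review, not on this table. All of that stands, and it rules out several stronger readings that a reader might infer:

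- That the primary laboratory endpoint as a whole is confounded. The step 5 comparison shows the defect in one summary, with a possible second.
- That this is the only categorical laboratory display. SAP 8.7.1 and 8.4.2 provide others.
- That the shift tables have been abandoned. They are absent from the SAP text, but the unseen table shells might contain them.
- That each cohort is spread over the five sites. The documents give the number of sites, not how cohorts are distributed among them. A cohort drawn mainly from one site would have little mixing of rules within it.
- That site criteria differ materially. The SAP allows it; the extent is unknown, and the criteria may be no more than local normal ranges.

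The reply does not dispose of the rest. The protocol asked for change-from-baseline statistics and shift tables together, so it did not treat one as a substitute for the other. Group summaries of eight can hide one subject's grade change and suit dipstick results poorly. Listings show individuals but do not summarise them. Placebo carries background too, but step 3 shows how weak two subjects are as a guard. Pooling placebo over five cohorts helps: at p = 0.10 the chance of at least one active and 0 of 10 placebo is 0.570 × 0.9^10 = 0.199. It still does not separate entry abnormalities from new ones.

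**Conclusion.** The concern holds in a limited form. As written, the by-visit summary in SAP 8.7.2 counts unchanged entry abnormalities and differences in site rules as post-dose abnormalities. The protocol's graded laboratory shift tables are missing from the SAP text, and their absence is not declared as a change. The effect is confined to that summary, plus the SAP 8.7.1 laboratory category if the site flag feeds it, which the SAP does not say. The documents do not support a finding that the whole laboratory endpoint mixes background with drug effect.

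The size is illustrative: 12.5 percentage points per active subject, with the step 2 to 4 figures resting on assumed rates and on flags that persist unchanged. The conclusion about the shift tables concerns the SAP text alone, since the shells were not seen. This should be corrected before the final analysis, but it does not threaten the trial's safety assessment as a whole.

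**What to change.** In SAP 8.7.2:

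1. Grade every gradable laboratory value by one programmed CTCAE v5.0 rule applied to all sites, using the performing laboratory's reference range where the grade depends on it. Some variation between laboratories will remain, and the SAP should say so.
2. Restore the protocol's shift tables: baseline grade by worst post-baseline grade, and baseline grade by grade at each visit.
3. Replace the count of flagged results with the number of subjects whose grade is new or worse than at baseline.
4. Keep the site flag for listings only, and state in SAP 8.7.1 how a result enters the laboratory-abnormality category.

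If the shift tables are deliberately not wanted, declare and justify that in SAP 8.0. If the table shells already contain them, name them in the SAP so that the two agree.

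The cost is SAP wording and programming. Protocol 7.5.1.4 and 7.5.2 list the same hematology, chemistry and dipstick tests at screening and follow-up, and normal ranges are already planned for the listings. No new data are needed and subjects are not affected.

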8.7.3 Vital signs

Visit values and changes from baseline for vital sign measurements (blood pressure, oral temperature, heart rate and respiratory rate) will be summarized by treatment group at each visit or timepoint using descriptive statistics. Visit values will be calculated as the mean of all available measurements per parameter. Subjects with vital signs will be listed and summarized by treatment group.

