7.3. Vital Signs

Vital sign assessments including systolic and diastolic blood pressure (BP) [measured after sitting for at least 10 minutes], heart rate (HR), respiratory rate, and oral temperature will be performed at each in-clinic study visit. Vital signs that are thought to be aberrant due to an error in measurement may be repeated. During screening and follow-up, a measurement that is a Grade 1 (as referenced in Appendix B by CTCAE version 5.0) may be repeated once if the PI believes a transient condition led to the aberrant value.

Vital signs obtained at screening will serve as baseline values for the subject. Grade 1 values are allowable unless deemed clinically significant by the study investigator.

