8.2. Visit 2: Baseline / Day of Dosing (Day 1)

Subjects meeting inclusion/exclusion criteria will be admitted to the clinical unit the day of injection and the following procedures will be performed prior to the study drug administration:

Prior to Dosing

- Review inclusion/exclusion to confirm eligibility
- Review CDC fact sheet on prevention of COVID-19 with subject
- Review and update concomitant medications and medical history
- Obtain vital signs
- Perform abbreviated physical examination with focused assessment for the presence of the following in order to detect signs of a hypersensitivity reaction:
 - General appearance including alertness, diaphoresis, chills, and any difficulty breathing.

- HEENT (confirm no swelling of lips/tongue/uvula)
- Chest (confirm no stridor or wheezing)
- Heart (assess regularity of rhythm)
- Skin (confirm no hives, examine for any eruptions)
- Joints (confirm no swelling, warmth, or tenderness)
- Perform Breathalyzer test or blood/saliva alcohol test to detect recent alcohol use
- Obtain urine sample for toxicology
- For women, a urine Hcg test will be done. The results must be confirmed to be negative before dosing
- Obtain blood samples for baseline serum PK and future use (for subjects who consent)
- Obtain blood sample for ADA
- Obtain blood sample for MN
- Obtain blood sample for RT-PCR testing
- Obtain blood sample for hypersensitivity panel
- Randomize the subject
- Obtain study product from the pharmacy
- Counsel both men and women of child-bearing potential on the avoidance of pregnancy

During Dosing

- Study product should be injected into the gluteus medius (see Appendix C). First divide the buttock in half from top to bottom and then in half from side to side. The injection should be given in the upper outer quarter.
- A study physician should be present at the time of study drug administration and the subject will be under direct observation during at least the initial 30 minutes after the injection by clinical study staff. The study staff should observe the subject closely for signs and symptoms of anaphylaxis and anaphylactoid type reactions. Should an adverse reaction of this type occur, the subject will be treated using the standard protocol at the site
- Obtain vital signs (blood pressure, heart rate, respiratory rate, and oral temperature) 15 (±3) minutes after the injection is completed.

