- Perform an abbreviated PE at 30 (±5) minutes post injection or in response to subject symptoms focusing on signs of anaphylaxis as follows:

- General appearance including alertness, diaphoresis, chills, and any difficulty breathing.
- HEENT (confirm no swelling of lips/tongue/uvula)
- Chest (confirm no stridor or wheezing)
- Heart (assess regularity of rhythm)
- Skin (confirm no hives, examine for any eruptions)
- Joints (confirm no swelling, warmth, or tenderness)
- Assessment of Aes and SAEs

Post Dosing

- Obtain vital signs (systolic and diastolic blood pressure, pulse rate, respiratory rate, and oral temperature) every hour (±10 min) for the first 2 hours after the completion of the injection and then every 2 hours (±10 min) for the next 4 hours. More frequent monitoring will be at the discretion of the PI based on the clinical presentation of the subject.
- Obtain blood samples for PK measurements at 2 h (±10 min), 4 h (±15 min), 8 h (±15 min) post injection.
- Obtain serum samples for future use (if consent given) at the following times after the end of injection, 2 h (±15 min), and 4 h (±15 min).
- Obtain a 12-lead ECG 30 minutes (±10 minutes) after completion of the injection.
- Assessment of Aes and SAEs

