8. A urine dipstick will be done to evaluate for presence of protein, glucose or blood in urine. If dipstick is abnormal, a complete urinalysis with microscopic will be performed.

9. A 12-lead ECG will be performed during screening and post dose performed 30 minutes (±10 minutes) after completion of dosing.

10. Viral Serology includes HIV, HBsAg and antibody to HCV.

11. PK samples will be taken at the following times: pre-dose, 2, 4, 8, and 24 hours post injection and on days 2, 3, 4, 8, 15, 30, 45, 60, 90, 120, 150, 180, and 365 for all cohorts

12. Serum from subjects who give consent for future use samples will be collected at 2 hr and 4 hr post dose and on days 2, 8, and 30

13. Vital signs (sitting for at least 10 minutes) will be checked just before injection and every visit.

14. The subject will be under direct observation during at least the initial 30 minutes of dosing. A physical examination will be performed at approximately 30 minutes post injection or in response to subject symptoms which will include the following: General appearance including alertness, diaphoresis, chills, and any difficulty breathing, HEENT, Chest, Heart, Skin and Joints

15. Draw prior to dosing at baseline

16. The Hypersensitivity Panel includes cytokine and complement panels, IgE, and tryptase. Draw 14ml prior to dosing. If a subject develops anaphylaxis or anaphylactoid reaction, an additional 10 mL sample will be drawn during the event and another will be drawn after the event

Protocol: ADM03820-001

Version 6.0 July 14, 2022

- 17. Subjects in all cohorts will receive RT-PCR testing at screening, Day 1 prior to dosing, and at presentation of symptoms.
- 18. SARS-CoV-2 antibodies will only be tested in Cohorts 1-4 (Not applicable for Cohort 5).

19. TC visits will be conducted for only Cohorts 1-4 (Not applicable for Cohort 5).

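### SAP 8.7.3 averages all vital-sign readings within a visit without limiting this to replicates, so the Day 1 summary may blend pre-dose and post-dose values and fail to show a brief change

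*SAP*

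**What the plan says.** SAP 8.7.3 states that vital-sign values and changes from baseline "will be summarized by treatment group at each visit or timepoint using descriptive statistics". The next sentence is the derivation rule: "Visit values will be calculated as the mean of all available measurements per parameter". The section names no Day 1 timepoints and does not say which measurements may be averaged together.

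The protocol places several readings inside Visit 2 (Day 1):

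- One before dosing. Section 8.2 lists vital signs among the pre-dose procedures, and a footnote to Appendix A says "Vital signs (sitting for at least 10 minutes) will be checked just before injection and every visit".
- One early reading, "15 (±3) minutes after the injection is completed" (section 8.2).
- A later series, "every hour (±10 min) for the first 2 hours after the completion of the injection and then every 2 hours", the two-hourly part running for a further 4 hours (section 8.2). Extra monitoring is at the investigator's discretion.

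Change from baseline in vital signs is one of the primary endpoints (Protocol 3.2.1; SAP, Study Endpoints). Protocol 11.3.3.2 adds a listing: "Subjects with Graded values of vital sign and laboratory parameters will be identified in listings". The matching sentence in SAP 8.7.3 has no reference to grade.

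**The concern.** The Day 1 series follows the injection closely, in the period when staff are told to watch for anaphylactic-type reactions. Such a change in blood pressure or heart rate may be short. If all Day 1 readings become one visit value, the reading that carries the change is averaged with later normal readings and with the pre-dose reading itself.

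The rule has little else to act on. Apart from Day 1, each in-clinic visit in the protocol lists vital signs once, and no replicates are scheduled. Safety endpoints are analysed descriptively, without tests, from eight active subjects per cohort, so the summary table is the planned analysis of this endpoint.

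**Working it through.** **The plan's own figures.** None depends on the averaging rule. The only numerical justification is in the sample-size section, and it reproduces: 1 − 0.85^8 = 0.7275 (stated 0.728), 1 − 0.5^8 = 0.9961 (stated 0.996), and an exact upper 95% limit for 0 of 8 of 1 − 0.025^(1/8) = 0.3694 (stated 0.369).

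**Scheduled Day 1 readings (Protocol 8.2).** Pre-dose (1) + 15 min (1) + 1 h and 2 h (2) + 4 h and 6 h (2) = 6, of which 5 are post-dose.

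**Effect of the mean.** Let p be the pre-dose value, b the baseline, and D a deviation from p present at k of the five post-dose readings, with the other readings at p.

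- Day 1 visit value = [(6 − k)p + k(p + D)]/6 = p + kD/6.
- Change from baseline = (p − b) + kD/6.
- If b = p, the change is kD/6.
- Summarised by timepoint with b = p, the change at an affected timepoint is D.

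The documents give no size for D. The values 20, 30 and 40 units are assumptions for illustration; the fractions follow from the schedule.

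| k of 5 | Kept | D = 20 | D = 30 | D = 40 |
|---|---|---|---|---|
| 1 | 1/6 (16.7%) | 3.3 | 5.0 | 6.7 |
| 2 | 2/6 (33.3%) | 6.7 | 10.0 | 13.3 |
| 3 | 3/6 (50.0%) | 10.0 | 15.0 | 20.0 |
| 4 | 4/6 (66.7%) | 13.3 | 20.0 | 26.7 |
| 5 | 5/6 (83.3%) | 16.7 | 25.0 | 33.3 |

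**Removing only the pre-dose reading is not enough.** The mean of five gives kD/5. For D = 30 that is 6, 12, 18, 24 and 30, so a single-reading change still appears at one fifth.

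**Which baseline applies.** The documents give three definitions for vital signs:

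- Protocol 7.3 and 11.3.3.2: the screening value.
- SAP Table 3 (Derived Variables): the latest value up to and including the dosing date.
- SAP, General statistical conventions: the most recent value before dosing.

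Under the third, b is the Day 1 pre-dose reading and the table applies. Under the first, b need not equal p; the offset p − b is carried unchanged and the post-dose deviation still contributes kD/6. Under the second, read literally, the 6 h reading could become the baseline. A change present at all five readings would then give b = p + D and a change of 5D/6 − D = −D/6, which has the wrong sign.

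**Extra readings.** The SAP keeps unscheduled points out of by-visit tables, while 8.7.3 averages everything available. It is not stated whether discretionary Day 1 readings enter the mean. If they do, the divisor exceeds six.

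**The case against.** The strongest reply is that SAP 8.7.3 already provides for timepoints. Day 1 is the visit with several scheduled vital-sign times, so the mention of a timepoint summary has little purpose if Day 1 is collapsed to one number. On that reading the mean applies only within a timepoint. This stands as a possible reading. A reader might infer that the Day 1 summary cannot show a transient change; the documents support only that the rule permits this, because it neither names the timepoints nor limits the averaging.

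A reader might also infer that acute reactions would be hidden from the safety assessment. They would not. Adverse events are collected during and after dosing and are primary endpoints themselves. SAP 8.7.6 lists and summarises hypersensitivity reactions, all subject data are listed individually, and the halting criteria in Protocol 9.5.1 work on events and their grade. None of these uses a visit mean.

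One sixth is the worst case, and the exact k/6 result needs baseline to equal the pre-dose value. Both points are right.

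Two further inferences go too far. Protocol 7.3 says "Vital signs that are thought to be aberrant due to an error in measurement may be repeated", which might suggest that an erroneous reading is averaged with its repeat. The documents do not say whether the first reading is retained or whether the repeat counts as unscheduled, so this cannot be established. And the SAP listing sentence without its grade qualifier might be taken to lose the graded values. Read literally it lists every subject: nothing is lost, but nothing is singled out. The SAP's section on changes from the protocol does not withdraw the protocol listing, so this looks like a dropped word.

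**Conclusion.** The point holds as a defect in a stated derivation rule. Applied as written, the rule pools one pre-dose and five post-dose readings, and the Day 1 descriptive summary of a primary endpoint may fail to show a brief change. The size is k/6 of the deviation, from 1/6 for one affected reading to 5/6 for all five. This assumes that only the six scheduled readings enter, that unaffected readings sit at the pre-dose level, and that baseline equals the pre-dose value. The harm is confined to the summary of visit values and changes. It should be corrected before the final tables are produced.

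**What to change.** In SAP 8.7.3:

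1. State that averaging applies only to replicate measurements of a parameter at the same scheduled timepoint.
2. Name the six Day 1 timepoints (pre-dose, 15 min, 1, 2, 4 and 6 h). Summarise each separately, with change from the pre-dose reading.
3. Add each subject's largest post-dose rise and largest post-dose fall on Day 1, summarised by treatment group.
4. Reconcile the vital-sign baseline across Protocol 7.3 and 11.3.3.2, SAP Table 3 and the SAP general conventions. If the result departs from the protocol's screening baseline, record it in the SAP section on changes to the planned analysis.
5. Restore the word graded in the listing sentence, so that it matches Protocol 11.3.3.2 and the laboratory wording in SAP 8.7.2.

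The readings are already scheduled by timepoint, so no new data are needed. The cost is SAP wording and a few more table rows.
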